11.1.1 Dose-Limiting Toxicities (DLTs)

Adverse events that are assessed by the investigator to be related to GEN3009, which occur during the DLT observation period of the Escalation Period as described in Section 5.8, and meet the specific criteria listed in protocol 7.1, are classified as DLTs. These criteria include: all Grade 5 toxicities; hematologic events including thrombocytopenia, neutropenia and anemia of Grades 3 or 4 and meeting certain additional criteria; and non-hematologic AEs of Grade 3 or higher excluding certain fevers, hypotension, laboratory values, nausea, vomiting, diarrhea, fatigue/asthenia, or alopecia, which meet certain additional criteria.

All DLTs will be listed, and summarized by SOC and PT.

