4.1.1 Dose Escalation

The Dose Escalation will consist of 10 DLs (including one optional intermediate dose level) as shown in [Figure 1](#).

The initial 3 DLs will be single-subject cohorts, which is the accelerated titration part of the Dose Escalation. The start of standard titration begins with the enrollment of the 3-subject cohorts at the fourth DL. Additional intermediate dose levels (eg, CCI mg) may also be explored based upon emerging data.

In the accelerated titration part of Dose Escalation, single-subject cohorts will be expanded to a 3-subject cohort if the subject experiences a grade ≥ 2 toxicity (ie, related AE), during the DLT evaluation period (ie, 28 days), or based on the decision of the sponsor's SC. When those subjects have completed their DLT evaluation period, the escalation model in Section [4.1.1.1](#) will be

initiated. If any single-subject cohort is expanded to a total of 3 subjects, all subsequent cohorts will initially have 3 subjects per cohort.

After all subjects within a DL cohort have completed the DLT evaluation period, the DEC will review the data and propose for initiation of the next DL cohort. The sponsor's SC will have to endorse the proposal before the next DL cohort can start dosing subjects. To supplement routine safety monitoring by the SC, as outlined in this protocol, a DMC will monitor safety data for the trial on a quarterly basis or more frequently as determined by the sponsor. Recommendations from the DEC, SC, and DMC will be based on evaluation of all available data including but not limited to clinical, safety, PK and pharmacodynamic data. Additional details regarding DEC, SC, and the DMC can be found in Sections 10.8 and 10.9.

The timeframe for dosing subjects in a DL cohort should proceed as follows:

- For an investigated, non-cleared DL, there should be at least 3 days between administration of the first dose to the first subject and the second subject within the same DL.
- Any additional subjects dosed in the investigated, non-cleared DL should receive their first dose at least 1 day apart.
- For a DL cleared for safety as recommended by the DEC/SC, there is no specific timeframe for subjects to receive their first dose (ie, additional subjects may be treated in parallel at the respective DLs that are considered safe).

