7 DOSE MODIFICATIONS AND SAFETY MANAGEMENT GUIDELINES

7.1 Dose-limiting Toxicities

7.2 Dose Escalation: Dose-limiting Toxicity

For the Dose Escalation, the DLT assessment period is defined as 28 days from the start of the first GEN3009 administration on C1D1.

The occurrence of any of the toxicities outlined in this section will be considered a DLT.

All Grade 5 toxicities

Hematologic:

- Thrombocytopenia Grade 4 ($<25.0 \times 10^9/\text{L}$ [$<25,000/\mu\text{L}$]) that is not due to underlying malignancy or extraneous cause
- Neutropenia Grade 4 ($<0.5 \times 10^9/\text{L}$ [$<500/\mu\text{L}$]) lasting >7 days **not attributable to underlying disease**
- Febrile neutropenia Grade 3 or 4 lasting >2 days (ie, absolute neutrophil count [ANC] $<1.0 \times 10^9 \text{ cells/L}$ with a single temperature of $>38.3^\circ\text{C}$ [100.9°F] or a sustained temperature of $\geq 38^\circ\text{C}$ [100.4°F] for more than 1 hour)
- Grade 3 or 4 hemorrhage associated with thrombocytopenia of \geq Grade 3 requiring platelet transfusion
- Anemia Grade 4.
- TLS Grade 4 (see [Appendix 4](#) for additional information)

Non-hematologic:

- All non-hematological AEs of grade ≥ 3 (severe or life-threatening), **excluding** the following:
 - a. Fever Grade 3 ($>40.0^\circ\text{C}$ [$>104.0^\circ\text{F}$]) for ≤ 24 hours
 - b. Hypotension Grade 3 (medical intervention indicated; hospitalization indicated) resolving in ≤ 24 hours
 - c. Laboratory values out of normal range that do not have any clinical consequence, are clinically transient in nature and that resolve in ≤ 3 days (including electrolyte abnormalities that respond to medical intervention)
 - d. Aspartate aminotransferase (AST) and/or alanine aminotransferase (ALT) Grade 3 returning to Grade 1 or baseline in ≤ 7 days
 - e. Nausea Grade 3 that responds to adequate antiemetic treatment in ≤ 3 days
 - f. Vomiting Grade 3 that responds to adequate antiemetic treatment in ≤ 3 days
 - g. Diarrhea Grade 3 that responds to adequate antidiarrheal treatment in ≤ 3 days
 - h. Fatigue/asthenia Grade 3 when fatigue/asthenia was present at baseline or that lasts for <14 days
 - i. Alopecia (no grading)

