Frequent laboratory monitoring of complete blood count including differential should be initiated to document start and resolution of hematological AEs. All AEs occurring during the defined DLT evaluation period will be assessed according to the criteria above. All AEs, including those not qualifying for a DLT, will be monitored and included in the evaluation of the toxicity profile of GEN3009 unless the event is clearly determined to be unrelated to GEN3009.

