11.4.1 Primary Endpoints

11.4.1.1 Escalation and Safety Run-in in Expansion

11.4.1.1.1 DLTs and AEs

- Number of DLTs during the DLT period (initial 28 days of treatment).
- Summary tables for AEs will include only AEs that started or worsened during the on-treatment period (the TEAEs).
- The incidence of TEAEs (new or worsening from baseline) will be summarized by system organ class and/or preferred term, severity (CTCAE grade), type of AE, and relationship to GEN3009 (Dose Escalation) or GEN3009 + GEN3013 (safety run-in).
- SAEs, non-serious AEs, and AESIs during the on-treatment period will be tabulated.
- All deaths (on treatment and post treatment) will be summarized.
- All AEs, deaths and SAEs (including those from the pre and post-treatment periods) will be listed and those collected during the pre-treatment and post-treatment periods will be flagged.

Further summaries of AEs will be specified in the SAP.

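### SAP 11.1.1 makes investigator-assessed relatedness a condition for a DLT while current protocol 7.2 and 7.3 state no such general condition, so the same events can give different DLT counts and Table 22 recommendations

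*SAP*

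**What the plan says.** SAP 11.1.1 sets three conditions for a DLT. The event must be among "Adverse events that are assessed by the investigator to be related to GEN3009, which occur during the DLT observation period", the window being that of the escalation period, and it must meet the criteria that the SAP locates in protocol 7.1. The SAP then paraphrases those criteria.

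In the current protocol, 7.1 is a heading without text. The escalation criteria are in 7.2 and the run-in criteria in 7.3. Section 7.2 opens with "The occurrence of any of the toxicities outlined in this section will be considered a DLT". Its broadest item is "All non-hematological AEs of grade" 3 or higher, followed by named exclusions, none of which concerns causality. It closes with "All AEs occurring during the defined DLT evaluation period will be assessed according to the criteria above". Within the list, attribution wording appears for two items only: Grade 4 thrombocytopenia ("that is not due to underlying malignancy or extraneous cause") and prolonged Grade 4 neutropenia. Febrile neutropenia, anemia, hemorrhage and TLS carry none there. Section 7.3 has the same structure.

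The DLT count is a primary endpoint of the Dose Escalation (protocol 11.4.1.1.1; SAP section 11) and the input to Table 22. SAP 1.1 names protocol v4.0 (Amendment 2) as its basis. SAP 2.1 lists the departures from that protocol, and a relatedness condition for DLTs is not among them.

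**The concern.** Read as written, the two documents classify the same event differently. Take a Grade 3 or 4 non-hematologic AE in the first 28 days that falls under none of the exclusions and that the investigator judges unrelated. It meets the protocol's list, but it is not a DLT under the SAP. Cohorts are small, the trial is open-label and uncontrolled, and safety experience with the drug is limited, so the causality judgement is uncertain and each event carries weight. At stake are the reported primary DLT rate and the mBOIN recommendation to escalate, remain, de-escalate or terminate. A reader of the final report could not tell which definition lay behind either.

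**Working it through.** **1. The plan's own decision rule.** Protocol 4.1.1.1 gives a target φ = 0.25, φ1 = 0.6φ = 0.15 and φ2 = 1.4φ = 0.35. The BOIN boundaries are:

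- λ1 = ln[(1−φ1)/(1−φ)] / ln[φ(1−φ1)/(φ1(1−φ))] = ln(0.85/0.75) / ln(0.2125/0.1125) = 0.1968
- λ2 = ln[(1−φ)/(1−φ2)] / ln[φ2(1−φ)/(φ(1−φ2))] = ln(0.75/0.65) / ln(0.2625/0.1625) = 0.2984

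These match the stated 0.197 and 0.298. A simulation of the design gave expected totals of 32.9, 32.0, 31.3 and 32.1 for the four scenarios of Table 34, against the stated 32.7, 32.0, 31.3 and 32.2. The rule has therefore been read as intended.

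**2. Direction.** With the listed criteria held the same, the SAP count equals the protocol count minus the subjects whose only qualifying events are judged unrelated. It can be lower than the protocol count but never higher.

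**3. Effect of one such subject on Table 22.**

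| Without relatedness condition | With it | Recommendation changes from → to |
|---|---|---|
| 1/3 | 0/3 | remain → escalate |
| 2/3 | 1/3 | de-escalate → remain |
| 3/3 | 2/3 | terminate → de-escalate |
| 2/6 (33.3%, above λ2) | 1/6 (16.7%, below λ1) | de-escalate → escalate |
| 2/9 (22.2%, between) | 1/9 (11.1%, below λ1) | remain, which stops escalation at 9 evaluable subjects → escalate |

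**4. How often this could happen.** The documents give no rate of unrelated events meeting the criteria, so the following is an illustration on assumed values. Let p be the probability that a subject has a related DLT. Let q be the probability that a subject without one has an event that meets the criteria and is judged unrelated. Subjects are independent. With three subjects every count from 0 to 3 leads to a different recommendation, so:

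- P(escalate after 3), with relatedness condition = (1−p)³
- P(escalate after 3), without it = [(1−p)(1−q)]³
- P(recommendations differ) = 1 − [1 − (1−p)q]³

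For p = 15%:

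| Assumed q | Escalate, with condition | Escalate, without | Recommendations differ |
|---|---|---|---|
| 3% | 0.85³ = 61.4% | 0.8245³ = 56.0% | 1 − 0.9745³ = 7.5% |
| 5% | 61.4% | 0.8075³ = 52.7% | 1 − 0.9575³ = 12.2% |
| 10% | 61.4% | 0.765³ = 44.8% | 1 − 0.915³ = 23.4% |
| 15% | 61.4% | 0.7225³ = 37.7% | 1 − 0.8725³ = 33.6% |

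For p between 5% and 25% and the same q, the chance of a different first-cohort recommendation runs from 6.6% (p = 25%, q = 3%) to 36.9% (p = 5%, q = 15%).

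**The case against.** The best counter-argument is that the protocol may presume relatedness. Section 4.1.1 speaks of "toxicity (ie, related AE), during the DLT evaluation period", and the cohort-size rule in 4.1.1.1 repeats that gloss. Section 7.2 then uses the word toxicities in its operative sentence and in its Grade 5 item. It also says AEs are "included in the evaluation of the toxicity profile of GEN3009 unless the event is clearly determined to be unrelated to GEN3009". This stands in part. Both glosses, however, belong to Grade 2 or higher triggers: expanding a single-subject cohort, and running the design on two evaluable subjects. The last sentence governs the toxicity profile, not DLT status, and sets a different standard from the SAP's. The largest DLT item refers to AEs. The protocol's intent is at best ambiguous, and ambiguity also calls for reconciliation.

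Four stronger readings are tempting, and the documents do not support them:

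- A reader might infer that the SAP added a filter the protocol never had. Protocol v4.0 is not available here, so the condition may have been carried forward from it.
- A reader might infer that unrelated events disappear and doses rise unchecked. Table 22 yields a recommendation. The dose escalation and safety committees weigh all available data, SAP 14.1 provides for TEAE summaries and AE listings, and SAP 11.1 tabulates all TEAEs of Grade 3 or higher whatever their relationship.
- A reader might call the lower count an error towards escalation. That assumes the all-cause count is the true one; counting events that really are unrelated would err the other way.
- A reader might infer that the SAP's mention of Grade 3 or 4 cytopenias widens the DLT list. The SAP qualifies it by further criteria and by its pointer to the protocol, so the paraphrase is loose but does not make a Grade 3 anemia a DLT.

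**Conclusion.** The inconsistency stands. The SAP conditions DLT status on investigator-assessed relatedness, and the current protocol states no general condition of that kind. A primary endpoint that also drives dose decisions therefore has two possible definitions, and one reclassified subject is enough to change the Table 22 recommendation at 3, 6 or 9 evaluable subjects. That result is exact. The probabilities (6.6% to 36.9% for a differing first-cohort recommendation) rest on assumed values of p and q, on independence between subjects and on the first three subjects only; they say nothing about final MTD selection.

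The SAP text names GEN3009 and the escalation only. For the combination run-in it supplies no DLT classification at all, and 7.3 stands alone until the SAP is updated.

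Protocol 2.1.4.1 reports no DLT among 18 evaluated subjects. A reader might infer that this zero depends on the relatedness condition. The documents do not say which definition was applied or whether any event was judged unrelated, so no such inference can be drawn.

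**What to change.** Reconcile SAP 11.1.1 with protocol 7.2 and 7.3 so that one DLT definition, with its causality condition stated explicitly, governs both the primary DLT rate and the mBOIN decision. Whichever definition the sponsor intends, both documents should state it in the same terms; this review does not say which it should be. Replace the outdated pointer to protocol 7.1 and the paraphrased grades with a direct reference to 7.2 and 7.3. List investigator causality beside every event that meets the criteria, and report the DLT count with and without the relatedness condition. The cost is a wording change, one extra listing column and one extra summary line.

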11.1.2 Adverse Events of Special Interest (AESI)

Adverse events of special interest (AESIs) may be identified throughout the course of the trial, and will include infusion-related reactions (IRRs).

TEAEs that are symptoms of AESIs may be summarized separately, with toxicity grades corresponding to the AESI category.

11.1.2.1 Infusion-Related Reactions (IRRs)

IRRs are defined as per protocol 10.1.4 as any AEs occurring during infusion or where the onset of the event occurs within 24 hours after the end of the infusion. Some events occurring within that window may be judged to not be infusion-related by the investigator.

All IRR signs and symptoms will be listed chronologically by subject. IRRs may be summarized by cycle and infusion number.

11.1.3 Deaths and Fatal AEs

Fatal adverse events will be summarized by dose level cohort or diagnosis cohort (as appropriate), SOC, and PT. All fatal adverse events will be presented in a separate listing, with post-treatment AEs flagged.

All deaths will be summarized by cohort, period (on-treatment or post-treatment), and primary cause of death. Death information will be listed by subject as well.

11.2 Vital signs and pulse oximetry

Actual values and change from baseline in vital signs will be summarized by cohort, period, visit and time point (where applicable). Oxygen saturation will be presented similarly.

The following clinically notable values will be flagged in listings. A separate table will present the number and percent of subjects meeting these criteria, by visit.

Clinically notable elevated values:

- Systolic BP: ≥ 180 mmHg and an increase ≥ 20 mmHg from baseline
- Diastolic BP: ≥ 105 mmHg and an increase ≥ 15 mmHg from baseline
- Weight: Increase of $\geq 10\%$ from baseline
- Heart rate: ≥ 120 bpm with an increase of ≥ 15 bpm from baseline
- Temperature: $> 38^\circ$ C

Clinically notable below normal values:

- Systolic BP: ≤ 90 mmHg and a decrease ≥ 20 mmHg from baseline
- Diastolic BP: ≤ 50 mmHg and a decrease ≥ 15 mmHg from baseline
- Weight: decrease of $\geq 10\%$ from baseline
- Heart rate: ≤ 50 bpm and a decrease ≥ 15 bpm from baseline
- Temperature: $< 35^\circ$ C

11.3 Clinical laboratory results

11.3.1 Haematology, chemistry, and urinalysis

Haematology, chemistry and urinalysis laboratory results will be graded programmatically as per CTCAE, where all results not meeting CTCAE grading criteria (for tests which are evaluated using CTCAE) will be assigned grade 0. The worst (highest) post-baseline CTCAE grade will be determined for each subject and laboratory test. Post-baseline labs will be defined by those recorded during the on-treatment period, as defined in Section 5.8.

For these laboratory tests where grades are not assigned via CTCAE, results will be categorized as low, normal, or high based on laboratory-provided normal ranges. If the laboratory provides categorizations in addition to normal ranges, laboratory-provided normality results will be used in lieu of programmatic categorization. The worst post-baseline normality classification will be determined for each subject and laboratory test, and will be considered the one furthest from the normal range boundary.

All recorded haematology, chemistry, and urinalysis results will be listed, with CTCAE grades or normality classifications indicated as applicable. Additional listings will present CTCAE grade 3 and 4 laboratory results.

Actual results and changes from baseline will be summarized by dose level cohort or diagnosis cohort (as appropriate), period, cycle, and study day.

For laboratory tests graded by CTCAE, shift tables will compare the baseline CTCAE grade to the worst post-baseline (e.g., worst on-treatment) CTCAE grade. Laboratory tests not graded by CTCAE will be presented using shift tables to evaluate the normality classification (low, normal, or high) at baseline as compared to the worst post-baseline (e.g., worst on-treatment) value.

A plot of the mean and standard error of each laboratory result will be displayed graphically over time.

11.3.2 Pregnancy test results

All laboratory results for pregnancy tests will be listed.

11.3.3 Serology

All laboratory results for HIV antibody, hepatitis B, hepatitis C, and cytomegalovirus (CMV) will be listed.

11.3.4 Tumor Lysis Syndrome Surveillance

All tumor lysis syndrome surveillance information will be listed by subject.

11.3.5 Tumor and bone marrow biopsy and aspirate results

All biopsy results will be listed chronologically by subject. Tumor biopsy and bone marrow biopsy and aspirate results will be listed separately.

11.3.6 Archived Tumor Tissue

All archival tumor tissue information will be listed by subject.

11.4 *ECG*

Electrocardiography results will be collected, and analysed by a central vendor.

QTcF will be categorized as defined in International Conference on Harmonization (ICH) E14: <=450 ms, >450-480 ms, >480-500 ms, and >= 500ms. Changes from baseline in QTcF will also be flagged if the changes are >30-60 ms or >60 ms.

Actual values and changes from baseline will be summarized by cohort, period and time point. In addition, the number and percent of subjects falling in each QTcF category, both for actual values and changes from baseline, will be presented. All electrocardiography results will also be listed chronologically.

11.5 *Physical Examination*

All available data will be listed, including performance of overall physical examination and date, and assessments of lymph nodes.

All abnormal findings will be recorded in medical history or adverse events, as appropriate. As such, summaries of abnormal findings will be included in medical history summaries (as per Section 7.3) or adverse event summaries (as per Section 11.1). No stand-alone summaries of physical examination results will be performed.

11.6 *ECOG*

All ECOG performance status results will be listed, and summarized by dose level cohort or diagnosis cohort (as appropriate), period and time point.

11.7 *Constitutional Symptoms*

All constitutional symptoms will be listed, and summarized by dose level cohort or diagnosis cohort (as appropriate), period and time point.

11.8 *Anti-Drug Antibodies*

The presence or absence of any anti-drug antibodies will be listed by subject and time point. The number and percent of subjects with anti-drug antibodies will be summarized overall and by time point.

Overall ADA status will be derived as follows:

- At least one positive result = "*positive for ADA*"
- No positive result, and at least one negative result and (may or may not have one or more indeterminate results) = "*negative for ADA*"
- Only indeterminate results, or no results = "*indeterminate*"

11.9 Hospitalization

All information regarding hospitalizations will be listed by subject.

11.10 Transfusions

All transfusion information will be listed by subject.

11.11 Chromosomal Alteration Status

All chromosomal alteration information will be listed by subject.

11.12 Radiographic Assessments

All FDG PET-CT scan (or CT/MRI and FDG PET when PET-CT scan not available) results will be listed.

11.13 Supplemental Safety Forms

Results of supplemental safety forms will be listed.

12 Biomarker Investigation

All biomarker results will be presented using the Safety Set, unless otherwise specified.

Results from circulating tumor DNA (ctDNA), DNA, RNA, and B-cell Receptor (BCR) clonality will not be listed or summarized herein, but will be presented in a separate biomarker technical report where appropriate.

12.1 Peripheral cytokine, complement and immunophenotyping measures

CCI

12.2 Protein Expression

CCI

13 Pharmacokinetic (PK) Analyses

Venous blood samples are collected prior to GEN3009 dosing, and specified time points after dosing, as described in Table 1-3 (Dose Escalation), Table 1-6 (Dose Expansion) and Section 9.5 of the protocol, for the measurement of plasma concentrations of GEN3009. Samples will also be collected at the End of Treatment visit.

The concentration of GEN3009 in plasma samples will be determined by a validated, specific, and sensitive ligand binding assay, at the assay CRO.

13.1 *The PK analysis and output to be generated are detailed in the next paragraphs. In short, GEN3009 concentration data will be presented graphically and summarized by dose group and ADA status. The sponsor will calculate PK parameters based on non-compartmental methods and will provide the results to be included in the Tables, Listings and Figures as part of this SAP. Graphical exploration of the relationships between exposure and covariates, observations of safety, efficacy or pharmacodynamic biomarkers will be performed by the sponsor outside of the scope of this SAP. GEN3009 Concentration data*

Individual observations of plasma concentration will be listed chronologically for each subject. Concentrations below the lower limit of quantification (LLOQ) will be reported as <LLOQ in data listings and omitted from summary statistics and graphs.

GEN3009 concentration data will be presented graphically, using individual curves of concentrations. All available data will be shown in these figures. Separate figures will be presented showing the plasma concentration-time profiles after the first dose of Cycle 1 and Cycle 2.

Concentrations will be summarized using both arithmetic and geometric means, standard deviations, coefficient of variations expressed as percentages (CV%), medians, minimums and maximums. Summaries will be presented overall and by ADA status, as described in Section 11.8.

